The Effects of computerized Cognitive Behavior Therapy (cCBT) on Brain Health: A feasibility study

PROTOCOL SUMMARY

Full Title	The Effects of computerized Cognitive Behavior Therapy (cCBT) on Brain Health : A feasibility study
Short title	HIV, depression and cCBT
Sponsor	McGill University
Funding	Canadian Institute of Health Research (CIHR)
Principal Investigators	[name], Department of Psychiatry, McGill University [name], Department of Psychiatry, McGill University [name], Department of Psychology, McGill University
Associate investigators	[name] [name]
Objectives	Among individuals with symptoms of depression and cognitive difficulties, and whose depression is treated with computerized Cognitive Behavioral Therapy (cCBT), to what extent is reduction in depressive symptoms associated with reduced reports of cognitive difficulties. Secondarily, to what extent is the reduction self reported cognitive difficulties concordant with improvement cognitive performance.
Study Population	Inclusion Criteria 
• Participants in the cohort study “Understanding and Optimizing Brain Health in HIV Now” with at least one remaining visit• Able to communicate (understand and read) in English• Depression subscale of the HADS (HADS-D) ≥ 8

The Effects of computerized Cognitive Behavior Therapy (cCBT) on Brain Health: A feasibility study

	
• Presence of self-reported cognitive difficulties (PDQ) ≥ 30• Score on the B-CAM > 14• Willing to undergo 9 sessions of cCBT as per instructions and to have weekly contact with a research coordinator from the central site (by email or phone)• Access to the internet 
Exclusion Criteria
 
• Current use of street drugs (excluding marijuana)
Study Design	Single cohort design with two repeated measures
Sample Size	30 participants have completed the intervention and the final evaluation
Participant involvement	Questionnaires at screening, pre- and post- intervention 9 sessions of cCBT plus regular contacts from the central site

The Effects of computerized Cognitive Behavior Therapy (cCBT) on Brain Health: A feasibility study

BACKGROUND

Among people living with HIV, challenges related to brain health are emerging. Brain health is a broad term referring to the inter-related factors of cognition, mood, anxiety, motivation, fatigue, stress and coping [1]. For example, among people with HIV, the severity of depressive symptoms has repeatedly been associated with the presence of self-reported cognitive difficulties, even in the absence of impairment on neuropsychological testing [2, 3]. There is uncertainty about the clinical importance of these self-reports, especially when neuropsychological testing is normal, as they are thought to be susceptible to patients' biases and insights into their illness.

However, there is growing evidence that these self-reports are clinically important. Among patients with major depressive disorder (MDD), evidence suggests that functional impairments is mediated by self-reported cognitive dysfunction, rather than objective cognitive dysfunction [4]. For example, Buist-Bouwman et al reported that more than one-quarter of the impact of MDD on work loss was directly attributable to self-reported cognitive difficulties and that cognition was a significant mediator of the association between MDD and work or role dysfunction [5].

When depression is treated with antidepressant medication, some degree of improvement on neuropsychological tests has been documented [6, 7] . However, many studies have evaluated cognitive outcomes before and after treatment rather than comparing them with placebo, potentially biasing the results by learning effects, which limits the strength of the conclusions that can be drawn.

Treatment of depression with Cognitive-Behaviour Therapy (CBT) has been shown to improve depressive symptoms and psychosocial functioning in patients with recurrent major depressive disorder [8], but there are few studies of the impact of psychotherapy on self-reported cognition and cognitive performance. In a group of patients with highly recurrent depression (≥ 4 episodes) over 2 years of follow-up, Conradi et al showed that those randomized to receive psycho-education plus CBT reported the presence of cognitive symptoms significantly less of the time compared to those receiving psycho-education only (15% of the time or 3.6 months compared to 47% or 11.3 months) [9].

The Effects of computerized Cognitive Behavior Therapy (cCBT) on Brain Health: A feasibility study

In the HIV population, a single study has examined the effect of treatment of depression on self-reported cognitive difficulties and performance on neuropsychological tests, as part of a randomized controlled trial of antidepressant efficacy [10]. Following 12 weeks of antidepressant treatment, HIV+ individuals who reported a decrease in depressive symptoms also reported significantly fewer cognitive difficulties, despite an absence of improvement on neuropsychological testing.

In the context where the use of questionnaires eliciting cognitive difficulties is suggested as a first-line screening for HIV-Associated Neurocognitive Disorder [11], it is important to document the clinical factors that influence these self-reports in order to inform their clinical interpretation and develop interventions for individuals reporting cognitive difficulties.

Understanding and Optimizing Brain Health Now (BHN) cohort study: Cohort participants (N=840) are studied prospectively over a 27-month period with visits every 9 months. Patients complete questionnaires on mood (Hospital Anxiety Depression Scale-HADS), presence of cognitive symptoms (Patient Deficit Questionnaire-PDQ), and a computer-based evaluation of cognitive ability (B-CAM) [12].

Computerized Cognitive-Behavioral Therapy (cCBT): A number of computerized treatment programs have been developed to address symptoms of depression and anxiety, and several meta-analyses of randomized controlled trials (RCTs) have shown evidence for their effectiveness [13, 14]. One such program, Good Days Ahead, teaches the basic principles of CBT in nine therapy sessions, each typically taking 30 minutes to complete. Good Days Ahead has been found to be as effective as face-to-face CBT in decreasing symptoms of depression and anxiety [15]. Patients receiving treatment delivered by a computer can be provided with different levels of guidance and support: self-guidance, guidance by a technician who sends reminders, or guidance by a clinician [13]. A recent meta-analysis of cCBT for depression and anxiety has shown that the treatment delivered with no guidance or support yielded, on average, a smaller effect size (Cohen's $d = 0.17$) than cCBT delivered with at least one hour of knowledgeable assistance during the course of therapy (Cohen's $d = 0.72$) [15]. Offering some assistance thus appears to be necessary for achieving better therapy outcomes.

STUDY OBJECTIVES

Among individuals with symptoms of depression who report cognitive difficulties and whose

The Effects of computerized Cognitive Behavior Therapy (cCBT) on Brain Health: A feasibility study

depression is treated with computerized Cognitive Behavioral Therapy (cCBT), to what extent is reduction in depressive symptoms associated with reduced reports of cognitive difficulties?

Secondarily, to what extent is the reduction in self-reported cognitive difficulties concordant with improvement cognitive performance?

STUDY HYPOTHESIS

The hypothesis is that people whose depressive symptoms are reduced following treatment with cCBT will also report fewer cognitive difficulties than before treatment. A second hypothesis is that changes in self-reported cognition will be concordant with changes in cognitive performance, such that people who make no improvement in self-report cognition will also show no improvement in cognitive performance and those who do improve on self-report will improve on cognitive performance.

STUDY DESIGN

This study is part of a larger project based upon a cohort multiple randomized controlled design [1]. Within a fully characterized cohort followed over time (n=840), people meeting the specific criteria for one or more interventions (here cCBT) are identified and a sample is randomly selected to receive the intervention. When the intervention is under investigation, the remaining eligible persons who do not receive the intervention serve as controls. In this study, we are not testing the effectiveness of cCBT as this has been demonstrated. Rather we are focusing on changes in cognition in relation to depressive symptoms mediated by cCBT. This study is an exploration of a hypothesis using a single cohort design with two repeated measures. For exploratory studies, an N of 30 optimizes an analysis based on means under the central limit theorem [16] .

POPULATION

Individuals who report depressive symptoms and self-reports of cognitive difficulties and who have agreed to be contacted for sub-studies will be invited to participate.

Inclusion criteria:

- Participant in the *Understanding and Optimizing Brain Health in HIV Now* (BHN) study

The Effects of computerized Cognitive Behavior Therapy (cCBT) on Brain Health: A feasibility study

- Able to communicate (understand and read) in English (Good Days Ahead software is only available in English)
- Score on the Hospital Anxiety and Depression Scale- depression subscale (HADS-D) ≥ 8
- Score on the Patient Deficit Questionnaire (PDQ) [17] ≥ 30
- B-CAM score > 14 to ensure that they can navigate the computer program
- Have not had changes in medication that could potentially interfere with mood and cognition, and are not expected to undergo such changes for the duration of the study
- Have been on a stable HAART regimen for > 6 months
- Willing to participate in cCBT as per instructions and to have regular contacts with the central site
- Have access to the internet
- Have at least one remaining visit in the main cohort study

Exclusion criteria:

- Current use of street drugs (excluding marijuana)

Potentially eligible participants will be identified from the BHN cohort and will be contacted by phone or e-mail (depending on the contact information provided by the participant) by a research coordinator at the central (Montreal) site who will introduce the study. Individuals who consent verbally will be asked to provide their email address. All participants will receive an e-mail with the informed consent document and will be instructed to return the e-mail to confirm consent to participate. Those consenting will be asked to complete on-line questionnaires (HADS and HIV-specific questionnaire of cognitive difficulties, the C3Q [18]) on a secure site to confirm eligibility and collect baseline information. Those remaining eligible will enter the intervention phase. People will be contacted and screened until a maximum of 36 participants have entered the intervention phase. This number was chosen as sample sizes around 30 for analysis are often used in exploratory studies to optimize an analysis based on comparison of means under the central limit theorem [16], and we except some drop outs from the cCBT therapy.

Intervention:

Participants who are eligible will receive online access to the Good Days Ahead cCBT program. Good Days Ahead is a learning module based on scientifically proven, evidence-based techniques. The program's content follows the teachings of the basic principles of CBT. The

The Effects of computerized Cognitive Behavior Therapy (cCBT) on Brain Health: A feasibility study

underlying platform generates customized learning experiences for each individual user with content including videos, text, quizzes and interactive exercises. The program comprises nine lessons of 30 minute each during which the user first learns the key concepts; then applies them to the program's main character who suffers from depression; and then applies those techniques to their own personal challenges (<http://www.empower-interactive.com/solutions/good-days-ahead>). Participants are expected to complete the nine sessions over 9-12 weeks.

As patients complete the cCBT program, their progress will be monitored by the research coordinator through a secure web site, using the program's dashboard feature that includes tracking of mood ratings, exercises, comprehension and completion rates. Participants will receive guidance during regular contacts by a trained research coordinator knowledgeable about the program and the basics of CBT.

MEASUREMENT

Three types of measures are under study: (i) depressive symptoms, (ii) self-reported cognitive difficulties; (ii) cognitive performance.

(i) Depressive symptoms will be measured using the Hospital Anxiety and Depression Scale (HADS) [19] before beginning and right after cCBT completion. It comprises two 7-item scales designed to rate depression and anxiety. It was developed to be brief, non-threatening and to exclude items which might reflect somatic symptoms. It has been widely used in research [20]. A score on the depression subscale (HADS-D) ≥ 8 is indicative of the presence of depression.

(ii) Self-reported cognitive difficulties will be measured using the C3Q collected before beginning and right after cCBT completion. The C3Q is a self-report measure of cognitive difficulties comprised of 18 items covering multiple cognitive domains. For each item, individuals rate the frequency of a cognitive difficulty on a three-point scale. The items fit the Rasch model, producing a legitimate total score with mathematical properties ranging from 0-36 with lower scores indicating more severe difficulties. C3Q has good content and construct validity and a good internal reliability (Person Separation Index 0.84) [18]. The mean score of C3Q among HIV+ individuals is 26.3 (SD: 8.2).

(iii) Cognitive performance will be measured by the B-CAM, a computerized test of cognition that yields a score on a continuous metric [21]. The B-CAM is administered at the regular BHN

The Effects of computerized Cognitive Behavior Therapy (cCBT) on Brain Health: A feasibility study

cohort visits. Two values will be used, those closest to the beginning and end of the CBT intervention period, usually 9 months apart.

STATISTICAL ANALYSIS AND SAMPLE SIZE

Basic descriptive statistics will be used to characterize the participants including values on all the outcomes.

To meet the first aim of linking change in depressive symptoms (as a result of cCBT) to change in self-reported cognitive difficulties, an analysis based on a comparison of two means will be carried out. The cCBT cohort will be classified as having changed on depressive symptoms if the score on the HADS-D has either fallen to below 8 or decreased by $\frac{1}{2}$ SD (2 points). The mean value of change on the C3Q will be compared between these two groups (depression improved vs no change), using an adjusted t-test based on linear regression, adjusted for covariates that differ between the two groups. This t-test is an estimate of between group effect size. The parameter of interest, however, is the within group effect size for cognitive change using the standardized response mean (SRM), which is the average within group change divided by the standard deviation of change. The two SRMs will be compared using relative effectiveness: SRM (depression improved group) / SRM (depression no change group)[16]. If this ratio exceeds 1.0, there is supportive evidence for a greater response in the depression improved group. This information on the between and within-effect sizes will be used to develop a fully powered study of this association.

The extent to which changes in self-reports are concordant with changes in cognitive performance will be assessed using percent agreement and 95% confidence intervals (CI). Each person will be classified as a responder or not based on change on the C3Q and on the B-CAM, with responder status defined as improvement of $\frac{1}{2}$ SD. This represents a change of 4 points on the C3Q and 2.3 points for the B-CAM. The table below shows the potential outcome patterns. If the value of c=0, all persons with decreased reports of cognitive difficulties also had improved cognitive performance with cCBT.

The Effects of computerized Cognitive Behavior Therapy (cCBT) on Brain Health: A feasibility study

		Cognitive difficulties C3Q	
		Decreased	no change
Cognitive performance B-CAM	improved	a	b
	no change	c	d

To illustrate, if 12 people among the 30 were concordant on response to the two types of cognitive measures, the estimate of concordance would be 0.40 with a 95% CI ranging from 0.25 to 0.58. This exploratory analysis will allow for comparison of characteristics between people who were concordant to those who were not.

POTENTIAL RISKS AND BENEFITS

There are no foreseeable risks associated with participating in the study. The intervention offered through this trial (Good Days Ahead) has already been shown to have positive effects on mood. Therefore similar clinical benefits will be expected in the population of the current study. Participants will receive compensation for their time, \$20 for completing the screening questionnaires and \$80 at the completion of the study.

ETHICS/ PROTECTION OF HUMAN SUBJECTS

Informed consent

All subjects will be given written information about the study and will confirm their consent to participate by e-mail prior to starting the study. Each subject will have sufficient opportunity to discuss the study and consider the information in the consent process prior to agreeing to participate. Subjects may withdraw consent at any time during the course of the trial. A copy of the consent e-mail will be retained in the subject's study files.

Participant Confidentiality

All records will be kept in a secure, locked location and only research staff will have access to the records. Each participant will be assigned an identification code for anonymously linking

The Effects of computerized Cognitive Behavior Therapy (cCBT) on Brain Health: A feasibility study

data. The identification information will only be accessible to the research coordinator in a password-protected document.

Upon request, clinical information may be reviewed by or released to auditors, CIHR or regulatory agencies. For participants who are invited to participate but refuse, the positive screen for the presence of depressive symptoms is communicated to the site PI as a “red flag” of potential significance for clinical care, according to a procedure already established in the *Brain Health Now* cohort study.

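### The N = 30 rationale describes the whole sample, but aim 1 compares two post-treatment groups of unplanned size, so its precision is unstated and lower than it need be

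*Combined protocol and SAP*

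**What the plan says.** The Study Design section states that, for exploratory work, "an N of 30 optimizes an analysis based on means under the central limit theorem". The Population section repeats the argument for the number recruited: "sample sizes around 30 for analysis are often used in exploratory studies to optimize an analysis based on comparison of means". Both refer to the total. The Protocol Summary sets the sample as "30 participants have completed the intervention and the final evaluation", and the Population section recruits until "a maximum of 36 participants have entered the intervention phase", allowing for an unspecified amount of dropout.

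In Statistical Analysis and Sample Size, the cohort is split after treatment: a participant counts as changed if HADS-D is now under 8 or has dropped by 2 points. Then: "The mean value of change on the C3Q will be compared between these two groups (depression improved vs no change"). The comparison is a covariate-adjusted t-test, followed by the ratio of the two groups' SRMs. The within-group SRM is named as the parameter of interest. The same section illustrates precision for aim 2 only: 12 of 30 concordant, 0.40, with a 95% CI of 0.25 to 0.58.

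**The concern.** The rationale and the aim 1 analysis refer to different quantities. About 30 people in total is offered as suited to "to optimize an analysis based on comparison of means under the central limit theorem", but the means being compared belong to two parts of that total. The parts are formed by an outcome, so their sizes cannot be fixed in advance, and the plan gives neither an expected share of improvers nor a smallest acceptable group.

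A central-limit argument concerns how close a mean is to normally distributed. It does not say how precisely a difference between two means will be estimated. Precision is what matters here, because the plan will use the between-group and within-group effect sizes to design a fully powered study. Cutting HADS-D change into two categories also discards information already collected, although the objective asks to what extent the two changes go together.

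**Working it through.** **The plan's own figures.** The aim 2 interval reproduces with the Wilson formula. With p = 0.40, n = 30 and z = 1.96, the limits are (0.400 + 0.064 ± 1.96 × √(0.00800 + 0.00107)) / 1.128 = 0.246 and 0.577, matching 0.25 to 0.58. The step from 30 to 36 fits 30 / (1 − 1/6) = 36, although no dropout rate is stated. The 30 itself cannot be reproduced: it is a convention, with no alpha, power, effect size, SD of change or split behind it.

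**Inputs for aim 1.**
- Total analysed: 30 (Protocol Summary).
- C3Q SD 8.2, cross-sectional, and Person Separation Index 0.84 (Measurement).
- Assumption: SD of C3Q change between 4.6 and 8.2. The lower value treats 0.84 as a reliability and lets change reflect measurement error alone: 8.2 × √(2 × (1 − 0.84)) = 4.64. The upper value is the cross-sectional SD.
- Assumption: splits of 15/15, 20/10 and 24/6, two-sided 5%, no covariates. Each covariate would use a further degree of freedom.

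**Precision of the difference.** Half-width = t(0.975, 28) × √(1/n1 + 1/n2) in SD units, with t = 2.048. Detectable difference and power come from the noncentral t distribution.

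| Split | √(1/n1 + 1/n2) | Half-width, SD | Points, SD 4.64 | Points, SD 8.2 | Detectable at 80% power, SD | Power at 0.5 SD |
|---|---|---|---|---|---|---|
| 15/15 | 0.365 | 0.75 | 3.5 | 6.1 | 1.06 | 26% |
| 20/10 | 0.387 | 0.79 | 3.7 | 6.5 | 1.12 | 24% |
| 24/6 | 0.456 | 0.93 | 4.3 | 7.7 | 1.32 | 18% |

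**How uneven the split could be.** Taking the number improved as binomial with n = 30, the chance that the smaller group has fewer than 10 people is 59% if 70% improve and 94% if 80% improve. Both shares are assumptions.

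**The SRM ratio.** In simulation with normal data and both true SRMs equal to 0.5, the middle 95% of ratios at 20/10 ran from about −5.6 to 8.8.

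**What the split costs.** Assume the two changes are linearly related and bivariate normal, with correlation 0.4 and N = 30. A slope fitted to everyone has about 61% power. The two-group t-test has about 42% at an even split and 32% at 80/20.

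**Limits of the slope.** For 80% power the required correlation satisfies atanh(r) = (1.960 + 0.842) / √27 = 0.539, so r is about 0.49. An observed correlation of 0.4 would have a 95% CI of tanh(0.424 ± 1.96/√27), or 0.05 to 0.66.

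**The case against.** The strongest reply is that the protocol promises nothing it fails to deliver. It calls itself an exploration of a hypothesis, presents 30 as a number often used in such studies, and defers power to a later study. That stands, so a reader should not infer that the study falls short of a power claim or needs more participants.

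Three other inferences also go too far:
- **That the t-test is invalid in small groups.** In simulation with skewed (exponential) data, type I error stayed between 4.5% and 5.0% at 15/15, 24/6 and 27/3. The central-limit wording is uninformative about precision, but it is not shown to be false.
- **That the plan says nothing else about sample size.** The aim 2 interval is a genuine precision statement. The gap is confined to aim 1.
- **That the interval fails a target set by the plan.** The 4 points on the C3Q is the individual responder threshold for aim 2, not a between-group difference for aim 1. As a borrowed yardstick it gives a mixed answer: at the lower assumed SD the half-width is under 4 points at 15/15 (3.5) and 20/10 (3.7), and over it at 24/6 (4.3).

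It is also fair to say that a slope is a different estimand from the within-group SRM, which the plan names as its parameter of interest. That is a reason to keep the SRMs. It does not remove the loss from dichotomising, because the slope answers the stated to-what-extent question directly and uses every participant.

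**Conclusion.** The concern holds in a limited form. The rationale for about 30 in total does not describe the precision of the aim 1 comparison, which is made between two groups of unplanned size. The likely half-width is 0.75 to 0.93 SD over splits from 15/15 to 24/6. In C3Q points that is 3.5 to 6.1 at 15/15 and 4.3 to 7.7 at 24/6. The point ranges rest on an SD of change of 4.6 to 8.2, which the documents do not give, and all the figures rest on the assumed splits and on no covariate adjustment.

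This is a weakness of justification and efficiency, not an arithmetic error or an invalid test. It merits a change because a more efficient analysis is available from data already planned: under the stated assumptions, about 61% power against 32% to 42%.

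**What to change.** In Statistical Analysis and Sample Size, add a linear regression of C3Q change on continuous HADS-D change in all participants, reported with its 95% CI, as the main between-person estimate for aim 1. State the expected sign, since higher C3Q and lower HADS-D scores are both improvements. Keep the improved versus no-change comparison and the within-group SRMs as supporting results.

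In Study Design and Population, replace the central-limit wording with the expected half-widths over plausible splits, and say that N = 30 is for estimation only. If 4 points is used as a yardstick, say that it is borrowed from the aim 2 individual responder threshold.

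The cost is a change in the lead aim 1 estimate, an assumption of a roughly linear relation, and a less favourable stated justification. Power stays limited at N = 30, since a correlation of about 0.49 is needed for 80%. No extra enrolment or data are needed.

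### The two B-CAM values need not bracket cCBT, and eligibility does not secure a cohort visit after it (minor; exploratory concordance table only)

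*Combined protocol and SAP*

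**What the plan says.** The selection rule is in Measurement (iii): "Two values will be used, those closest to the beginning and end of the CBT intervention period, usually 9 months apart". The scores come only from the parent cohort's own schedule: "The B-CAM is administered at the regular BHN" cohort visits. The Background gives that schedule: "Cohort participants (N=840) are studied prospectively over a 27-month period with visits every 9 months". The Intervention section gives the length of treatment: "Participants are expected to complete the nine sessions over 9-12 weeks".

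Eligibility mentions visits twice. The Protocol Summary admits cohort participants "with at least one remaining visit". The Population section lists "Have at least one remaining visit in the main cohort study". Neither says when that visit must fall relative to cCBT. Recruitment is described by number only, with no link to visit dates: "People will be contacted and screened until a maximum of 36 participants have entered the intervention phase".

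Self-report is handled differently. Measurement (ii) states: "Self-reported cognitive difficulties will be measured using the C3Q collected before beginning and right after cCBT completion". The depression scale has the same before-and-after timing.

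Statistical Analysis and Sample Size then classifies each person as a responder or not on C3Q change (4 points) and on B-CAM change (2.3 points), and cross-tabulates the two. It reads an empty cell c as showing that everyone with fewer reported difficulties also performed better under treatment.

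**The concern.** The table sets two changes side by side as though both described the effect of treatment. The C3Q change always spans the whole of cCBT. The B-CAM change does so only if one cohort visit comes before cCBT and the other after it, and no passage makes that a condition.

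Two gaps follow:

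- If a visit falls during cCBT, its score can be paired with the previous visit (as post) or with the next visit (as pre). The plan does not say which. Either way, only part of treatment is covered.
- If that visit is the person's last, no post-treatment B-CAM will exist, although the person met the eligibility criteria.

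B-CAM responder status can then be misclassified, and each person moved between agreement and disagreement shifts the estimate by 1/30 = 3.3 percentage points. The planned comparison of concordant with non-concordant people would inherit the error.

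**Working it through.** **Inputs.** Visit spacing is 9 months, or 9 × 52/12 = 39 weeks, over 27 months = 117 weeks (Background). cCBT length D is 9 to 12 weeks (Intervention). The illustrative result is 12 of 30 concordant (Statistical Analysis and Sample Size). Start dates relative to visits are not given, so every share below rests on an assumption.

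**The plan's own figure.** The Wilson interval for 12/30, with z = 1.96:

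- centre = (0.40 + 3.84/60) / (1 + 3.84/30) = 0.411
- half-width = 1.96 × √(0.24/30 + 3.84/3600) / 1.128 = 0.165
- interval = 0.246 to 0.577, which agrees with the stated 0.25 to 0.58.

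**Which visit is nearest.** A visit during cCBT is at most D ≤ 12 weeks from the start and from the end. The previous and next visits are each at least 39 − 12 = 27 weeks from either. With visits on schedule, the mid-treatment visit is therefore always nearest to both ends. Getting two values means adding a neighbouring visit, and the plan does not say which one.

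**How often a visit falls during cCBT.** If starts are uniform over the first x weeks after a visit, the share is max(0, (x − (39 − D))/x).

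| Starts spread over | D = 9 | D = 12 |
|---|---|---|
| 27 weeks | 0% | 0% |
| 30 weeks | 0% | 3/30 = 10% |
| 33 weeks | 3/33 = 9% | 6/33 = 18% |
| 39 weeks | 9/39 = 23% | 12/39 = 31% |

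The last row is about 7 to 9 people of 30.

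**How much of treatment is covered.** Let the visit fall a fraction f of the way through cCBT. The earlier pair covers f and the later pair covers 1 − f. With f uniform, the nearer pair covers 50% to 100% (mean 75%), and its mid-treatment score is misplaced by D/4 = 2.25 to 3 weeks on average. The other pair covers 0% to 50% (mean 25%). If the mid-treatment visit is the last, the only pair covers f (mean 50%).

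**No post-treatment score.** Assume visits at 0, 39, 78 and 117 weeks and starts uniform over 117 weeks. The share is D/117 = 9/117 to 12/117, or 8% to 10%. Among people with exactly one remaining visit it is D/39, or 23% to 31%.

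**What strict bracketing would do.** Suppose eligibility required a visit after cCBT, so that starts run from 0 to 117 − D weeks. A person with a mid-treatment visit would then have an 18-month pair. The share is 2D/(117 − D) = 18/108 to 24/105, or 17% to 23% (5 to 7 of 30). The two values in such a pair lie on average (78 − D)/2 = 34.5 to 33 weeks outside cCBT. Excluding these people leaves about 25 to 23 of 30. Near 40% agreement the Wilson interval is 0.23 to 0.59 (10/25) or 0.22 to 0.59 (9/23).

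**The case against.** The natural reading answers most of this. Two values tied to the two ends of treatment and usually 9 months apart suggest the previous visit and the next. The B-CAM entry threshold implies that an earlier score exists, and the remaining-visit criterion was probably meant to supply the later one. Strict nearest-visit selection cannot be what was meant: under uniform starts it would pick the same visit for both ends in 1 − D/39 = 69% to 77% of cases. When it does pick two different on-schedule visits, they bracket cCBT. This stands, and it means the plan lacks an ordering rule and a tie-break. A reader might infer that the plan directs the use of mid-treatment scores; the documents do not say that.

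The size is also assumed. Candidates are identified from cohort data, and if starts follow visits closely the share is zero. A reader might infer that a quarter or more of the table is compromised, but nothing in the documents establishes uniform starts.

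The Protocol Summary counts 30 people who have completed the final evaluation, which might exclude anyone without a post B-CAM. That term is undefined and may mean only the post-treatment questionnaires, so it does not close the gap.

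Finally, strict bracketing can cost more than it gains. For someone with a mid-treatment visit it swaps a 9-month pair covering 75% of treatment on average for an 18-month pair containing much untreated time. That is fair, and the fix leaves the choice between the two pairs open.

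**Conclusion.** The gap in the text is certain: neither the selection rule nor the eligibility rule secures a B-CAM pair that brackets cCBT, and no other passage does. Its size is not derivable. It ranges from 0% if everyone starts within 27 weeks after a visit to 23% to 31% if starts are uniform between visits, with visits on schedule and cCBT taking 9 to 12 weeks. Most people are likely to have a bracketing pair.

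A reader might go further and infer that the concordance estimate is biased in a known direction, or that the main result is in doubt. Neither follows. The documents give no basis for the direction of error, and the first aim uses the depression scale and the C3Q, both tied to treatment. Only the secondary, exploratory table is affected. Severity: minor.

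**What to change.** 1. **Eligibility** (Protocol Summary and Population): require at least one remaining cohort visit scheduled after the expected end of cCBT.
2. **Selection rule** (Measurement (iii)): define pre as the last cohort B-CAM on or before the start of cCBT, and post as the first on or after its end. Report the gap from the end of cCBT to the post value; even 9-month bracketing pairs allow up to 39 − D = 27 to 30 weeks. Report how many people have no post value, since overruns and missed visits can still cause some.
3. **Visits during cCBT**: choose in advance between the 18-month bracketing pair and the nearer 9-month pair, state the choice, and report how many people it affects. Show the concordance once more with these people excluded.

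The cost is a clause in two places, a few sentences in Measurement and the analysis section, and one sensitivity analysis, all on existing cohort visits. The eligible pool shrinks by about 8% to 10% if starts are uniform over 27 months. The sensitivity analysis loses little precision, with an interval of roughly 0.22 to 0.59 against the stated 0.25 to 0.58.
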